10.9 Visit Windowing

Subjects are expected to attend daily visits until hospital discharge. Visits will be re-initiated in case of a COVID-19 related hospital re-admission. Subjects who do not discharge will have daily assessments up to Day 29. Subjects who do discharge will have visits Day 8, 15, 22, 29, 60. All subjects will have a follow-up visit at Day 60.

No visit windowing will occur for the 8-point ordinal scale. Daily values for the 8-point ordinal scale will be assigned based on the trial day the assessment occurs i.e. the value recorded on trial day X will be assigned as the value of the ordinal scale at Day X in the analysis. For discharged subjects, information on the oxygen use at home between visits will be entered on the concomitant medication page and the daily 8-point ordinal scale value for discharged subjects will be derived. If a subject has oxygen use on a trial day as per Section 10.10, they will be assigned a value of 2 on the adjusted 8-point ordinal scale (refer to Table 3 in Section 10.8) on the trial days between the oxygen start and end day. If Day 29 occurs on trial day greater than 29, for the analysis purposes a value of Day 29 will be assigned. For Day 60 the value collected at the Day 60 visit will be used in the analysis, even if this did not occur on trial Day 60. All endpoints for the 8-point ordinal scale will summarize Day 8, 15, 22, 29 and were applicable Day 60 time points. If a subject has multiple non-missing ordinal scale assessments on a trial day the assessment that occurred on the scheduled visit per the eCRF will be used in the analysis.

For hospitalized subjects, vital signs, supplemental oxygen use and oxygen saturation will be collected daily. Therefore, no visit windows will be assigned and results in the analysis will be summarized for each trial day up to Day 29. Trial day calculation is defined in Section 10.2. If the trial day an assessment occurs on does not align with the visit trial day in the CRF, the trial day will take precedence in terms of analysis. Laboratory assessments (including CRP and LDH) will be conducted while in hospital but not daily. Analysis visit windows as defined in Table 4 will be used for laboratory assessments. If a subject has multiple assessments in a window, the visit closest to the target day will be selected. For visits that are equally close to the target day, the assessment latest in time will be selected.

An early withdrawal visit (EWD) will be conducted for subjects who discontinue the trial prior to Day 15. This visit will be mapped to analysis visits per Table 4 and to a daily time point based on the trial day the assessment occurs. If a scheduled visit and EWD occur on the same day, the scheduled visit will be used in the analysis for the 8-point ordinal scale.

Table 4: Visit Windowing for Laboratory Assessments and CRP/LDH

Visit	Target Trial Day	Lower Limit	Upper Limit
Baseline	1		1 (pre-baseline)
Day 3	3	1 (post-baseline)	3
Day 5	5	4	6
Day 8	8	7	9
Day 11	11	10	12
Day 15	15	13	16

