10.7 Imputation of Missing Dates

There will be no imputation of partial and missing dates. Duration of events will not be calculated if start or stop date is partial and listings will display the collected date and not the imputed date. The following rules will be implemented to determine the assignment of AEs as TEAE and therapies as prior and concomitant for the analysis.

In general, in such cases an AE will be considered treatment-emergent, unless there is evidence in the (partial) dates available that it was not treatment-emergent. In particular, in case of missing start dates of AEs, these will be considered treatment-emergent, unless the stop date of the AE is prior to the first dose of IMP. In the case of partially missing start dates, the AE will be considered treatment-emergent, unless the information from the partial dates clearly shows that the AE was not treatment-emergent i.e. the year/month is prior to treatment start date.

For therapies if start date is missing and the end date is prior to the first dose of IMP, the therapy will be considered prior. If start date is missing or partial and the end date is missing or after first dose of IMP, the therapy will be considered both prior and concomitant unless there is evidence in the partial dates that clearly classifies the therapy as prior or concomitant (i.e. start year/month is after the first date of IMP). If end date is partial or missing and start date is after first dose of IMP the therapy will be considered concomitant.

10.8 8-point Ordinal Scale

The clinical status of COVID-19 is scored at each visit according to the 8-point ordinal scale. For hospitalized subjects this will be assessed by the investigator once daily until Day 29. For discharged subjects the 8-point ordinal scale will be assessed at Day 8, Day 15, Day 22, Day 29 and Day 60. Discharged subjects will be assessed for daily supplemental oxygen use since the previous visit. If there was supplemental oxygen use on the days between visits, the subject will be considered to be on oxygen on those days and an 8-point ordinal scale score of 2. For further details on the assessment of supplemental oxygen use for discharged subjects please refer to Section 10.10.

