12.5.4 Other Secondary Endpoints

Other secondary endpoints assessing proportion of subjects will be compared using similar logistic regression models as described in Appendix 2 with the treatment effect expressed as a difference in proportions. Difference in proportions by treatment (intervention – placebo) will be estimated and 95% CI will be provided. Death prior to endpoint readout will be handled as worst case, that is subject will be assumed to be in mechanical ventilator need, or to be in oxygen need, or not to have fulfilled an improvement of 1 or 2 units. Subjects in ventilator need at readout will be considered in oxygen need. Unless otherwise specified missing data will not be multiply imputed. These secondary endpoints include:

- 1) Proportion of subjects discharged from hospital and free of supplemental oxygen at Days 8, 22 and 29. Missing data will be imputed as per Section 10.19.1.

- 2) Proportion of hospitalized subjects on non-invasive, invasive mechanical ventilation, ECMO or supplemental oxygen use at Days 8, 15, 22, 29 and 60. Missing data will be imputed as per Section 10.19.1.
- 3) Proportions of subjects in each category of the 8-point ordinal scale at Days 8, 15, 22, 29 and 60. This will be based on the complete case (where deaths are considered in category 8 following date of death). This will be the actual recorded 8-point ordinal scale and not the adjusted scale. This analysis will be descriptive only.
- 4) Proportions of subjects in each category of the adjusted 8-point ordinal scale at Days 8, 15, 22, 29 and 60. This will be based on the average of values from each imputed dataset created per the analysis in Section 10.19.1.
- 5) Proportion of subjects needing intensive care unit stay at Days 8, 15, 22, 29 and 60. Deaths will be considered in ICU following date of death. Only documented ICU stay will be considered. Subjects with no documented ICU stay will be included as 0 days.
- 6) Proportion of subjects on invasive mechanical ventilation or ECMO at Days 8, 15, 22, 29 and 60, and duration of use up to Day 60. Missing data will be imputed as per Section 10.19.1.
- 7) Proportion of subjects free of respiratory failure at Days 8, 22, 29 and 60. This data will be imputed as per Section 10.19.1.

Respiratory failure free days up to Day 60 (refer to Section 10.14) will be analyzed as using a Wilcoxon rank-sum test per the key secondary endpoint oxygen supplemental free days up to Day 29.

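### Exact-day assignment of ordinal scores (SAP 10.9) drops on-schedule discharged subjects from the recorded-scale category table in SAP 12.5.4 item 3, while inpatients and deaths stay in

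*SAP*

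**What the plan says.** Four parts of the plan meet here.

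- **Scoring schedule (SAP 10.8).** Inpatients: "For hospitalized subjects this will be assessed by the investigator once daily until Day 29". After discharge: "For discharged subjects the 8-point ordinal scale will be assessed at Day 8, Day 15, Day 22, Day 29 and Day 60".
- **Visit windows (schedule of activities, Protocol 1.3 and SAP Table 1).** Day 15 may fall one day late. Days 22 and 29 may each fall one day either side. Day 60 has ±3 days. The Day 8 visit has no window of its own; the ±1 day shown there belongs to laboratory samples.
- **Assignment to analysis days (SAP 10.9).** "No visit windowing will occur for the 8-point ordinal scale"; instead, "the value recorded on trial day X will be assigned as the value of the ordinal scale at Day X in the analysis". There are two exceptions. One concerns late Day 29 visits: "If Day 29 occurs on trial day greater than 29, for the analysis purposes a value of Day 29 will be assigned". The other is that the score from the last follow-up visit counts for Day 60 whatever trial day it was taken on.
- **The table (SAP 12.5.4 item 3).** Proportions in each category at Days 8, 15, 22, 29 and 60, a secondary efficacy endpoint listed in Protocol section 3 and SAP 9.2.2. On missing data and deaths the SAP says: "This will be based on the complete case (where deaths are considered in category 8 following date of death"). On the scale it says: "This will be the actual recorded 8-point ordinal scale and not the adjusted scale". The SAP labels the analysis descriptive.

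**The concern.** Whether a subject is counted in item 3 at Day 15, 22 or 29 depends partly on outcome. An inpatient is scored every day and so has a score on the target day. A death is carried forward as category 8. A discharged subject has a score on the target day only if the contact happened on exactly that day, although the schedule allows a day either side (or one day late, for Day 15). The subjects lost are all in categories 1 or 2, so the complete-case percentages shift towards the inpatient categories and death for reasons of visit timing.

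What is at stake is a misleading picture of clinical status in a listed secondary endpoint. Category 8 in this table can also differ from the all-cause mortality proportions that 12.5.4 presents for the same days.

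**Working it through.** **Which visits are lost.** Set the windows against the rule in 10.9:

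| Visit | Allowed trial days | Assigned to nominal day | Lost from item 3 |
|---|---|---|---|
| Day 15 | 15, 16 | 15 | 16 |
| Day 22 | 21, 22, 23 | 22 | 21, 23 |
| Day 29 | 28, 29, 30 | 29, 30 | 28 |
| Day 60 | 57 to 63 | all | none |

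The laboratory rule differs: SAP Table 4 accepts trial days 13 to 16 for Day 15. A clinic visit on day 16 therefore supplies Day 15 laboratory values, but its recorded ordinal score does not count for Day 15 in item 3.

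**Whether derived daily values fill the gap.** SAP 10.9 provides for deriving daily values after discharge. The rules that do so (10.9, 10.10 and 10.19.1) build the adjusted scale, which item 3 excludes.

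**Size.** The plan states no figure to reproduce. Let d, h and m be the true proportions discharged, inpatient and dead, and g the share of discharged subjects seen in window but on a day that is not mapped. Then:

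- share of subjects retained = 1 − g·d
- shown discharged = d(1 − g) / (1 − g·d)
- shown inpatient = h / (1 − g·d)
- shown dead = m / (1 − g·d)

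Assumed Day 22 status: d = 0.80, h = 0.12, m = 0.08. The documents give neither these proportions nor g.

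| g | 1 − g·d | Discharged | Inpatient | Dead |
|---|---|---|---|---|
| 0 | 1.000 | 80.0% | 12.0% | 8.0% |
| 0.10 | 0.920 | 78.3% | 13.0% | 8.7% |
| 0.20 | 0.840 | 76.2% | 14.3% | 9.5% |
| 1/3 | 0.733 | 72.7% | 16.4% | 10.9% |
| 2/3 | 0.467 | 57.1% | 25.7% | 17.1% |

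The last row corresponds to Day 22 contacts spread evenly over the three allowed days.

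Varying d with m held at 0.08:

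- d = 0.70: shown discharged is 0.63/0.93 = 67.7% at g = 0.10, and 0.233/0.533 = 43.8% at g = 2/3.
- d = 0.85: it is 0.765/0.915 = 83.6% at g = 0.10, and 0.283/0.433 = 65.4% at g = 2/3.

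Every retained category is inflated by the same factor, 1/(1 − g·d), whatever the death proportion. At d = 0.80 the factor is 1.09 for g = 0.10 and 2.14 for g = 2/3.

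**Side-by-side illustration.** Take 150 per arm, the sample-size section's Day 60 death proportions (10% placebo, 2.5% C21) as stand-ins for Day 22, an assumed 10% inpatients per arm, and the same g in both arms. The true category 8 gap is 7.5 points.

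| g | Placebo dead | C21 dead | Gap | N placebo / C21 |
|---|---|---|---|---|
| 0.10 | 10.9% | 2.7% | 8.1 points | 138 / 137 |
| 1/3 | 13.6% | 3.5% | 10.1 points | 110 / 106 |
| 2/3 | 21.4% | 6.0% | 15.4 points | 70 / 62.5 |

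**The case against.** **Reach.** Item 3 is one descriptive table with no test and no place in the testing hierarchy. This stands. A reader might infer that confirmatory results are biased too; the documents do not support that. The primary analysis uses death dates (10.11), and time to sustained discharge uses discharge dates (10.12). The oxygen-free-days and Day 15 endpoints draw on the adjusted scale derived for days after discharge, with multiple imputation (10.10, 10.19.1), so these subjects are not dropped.

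**Item 4 already gives the proportions with these subjects included.** It does, on the adjusted scale averaged over imputed datasets. Items 3 and 4 would differ anyway, because item 4 remaps score 2 without oxygen to 1 and imputes missing data; disagreement between them is not in itself evidence of error. But item 4 does not correct item 3, which is meant to show the scale as recorded.

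**Text that might rescue the subjects.** The 10.9 sentence on deriving daily values does not itself say adjusted, and 10.8 gives home-oxygen days a score of 2. Item 3's insistence on the recorded scale weighs against using derived values. Even on the generous reading, 10.8 would help only home-oxygen users.

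**Size.** The 57% and 17% figures need two thirds of discharged contacts to miss the target day. Nothing in the documents supports an even spread, and a tolerance of one day around a phone or video contact may well be used little. The assumed 8% dead also exceeds the plan's own pooled Day 60 expectation, (10% + 2.5%)/2 = 6.25%. Both points stand: the large figures are an upper illustration, not an expectation.

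**Conclusion.** The gap is real but narrow. Followed as written, 10.9 and 12.5.4 item 3 remove discharged subjects seen on schedule on trial day 16, 21, 23 or 28, and keep inpatients and deaths. Within each arm the direction is fixed whenever any such visit occurs: categories 1-2 are too low, inpatient and death categories too high.

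The size cannot be read from the documents. Under the assumed 80/12/8 status at Day 22 it runs from under 2 points on the discharged share (g = 0.10) to about 23 points (g = 2/3), and it vanishes if all contacts fall on the target day.

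A reader might also infer that subjects are lost simply for doing well. They are lost only if discharged and also seen off the target day. Day 60 is protected, and a loss at Day 8 would need a visit outside the schedule. No hypothesis test is affected. It should be corrected because the table reports a listed secondary endpoint and the correction is cheap.

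**What to change.** Add to SAP 12.5.4 item 3, for the recorded-scale table only:

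- For discharged subjects, use the score from the eCRF scheduled visit at its nominal day when the visit falls in the protocol window (Day 15: trial days 15-16; Day 22: 21-23; Day 29: 28-30).
- A score recorded on the target day itself takes precedence.
- Report N per arm and time point.

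This extends what 10.9 already does for late Day 29 and Day 60 visits. It belongs in item 3 because 10.9 governs all ordinal-scale analyses: a change there would move day 16 scores into Day 15 on the adjusted scale, touch the Day 15 key secondary endpoints, and possibly conflict with oxygen status derived for the actual day. Leave that derivation unchanged.

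The cost is a few lines of text and one programming rule before unblinding. The small downside is that some scores will be one day off target.

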10.10 Supplemental Oxygen Use

Hospitalized subjects will be assessed on a daily basis for their oxygen use. If a subject is discharged, they may be prescribed supplemental oxygen for at-home use. On each visit following discharge a subject will be assessed if they have used oxygen since the last visit and which days and if they have used supplemental oxygen this will be recorded on the concomitant medication page of the CRF. Subjects who have used supplemental oxygen since the previous visit will also be assessed if they are still on oxygen at the visit.

If a subject has a scheduled ordinal scale score of 1, 3, or 4 (i.e. free of supplemental oxygen use) and there is evidence of supplemental oxygen usage, the value on the adjusted ordinal scale will not be changed and the investigator's judgement will be considered the most accurate assessment of clinical status. The collected ordinal scale value will be used as the value in the analysis and the subject will be considered free of supplement oxygen usage on the trial day of interest.

For discharged subjects, the daily oxygen use will be derived. If a subject has oxygen use on a trial day they will be assigned a value of 2 on the adjusted 8-point ordinal scale on the trial days between the oxygen start and end day. A discharged subject will be considered to be using supplemental oxygen on a trial day if:

1. The subject has a record at the time point for supplemental oxygen use on the Oxygen supplementation during oxygen saturation measurement page of the CRF.
2. The subject has "Yes" at a time point to the question "Was subject still on COVID-19 related supplemental oxygen at the time of visit" on the Visit page of the CRF for discharged subjects at Day 8, Day 22, Day 29 and Day 60 and on the End of Treatment page for Day 15.
3. If a subject has a missing ordinal scale score on the day of discharge or a value of 2 on the ordinal scale and on the Hospitalization CRF page the question "Was COVID-19 related supplemental oxygen for at home use prescribed?" is Yes then a subject will be considered on supplemental oxygen at discharge and the visit that corresponds with discharge.
4. Subject has a record on the concomitant medication page for post-baseline supplemental oxygen use (preferred term entered as Oxygen and the therapy is concomitant per Section 10.5)

Otherwise the subject will be considered oxygen free at a time point. If the subject has an ordinal scale score of 2 at these time points and is not on supplemental oxygen they will be assigned an adjusted ordinal scale score of 1.

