
 • To explore the effect of C21 versus placebo as add on to SoC on inflammation. 	
 • Change from baseline in CRP at Day 15.

 • To explore the effect of C21 versus placebo as add on to SoC on lung injury. 	
 • Change from baseline in lactate dehydrogenase (LDH) at Day 15.

Primary estimand

All-cause mortality up to Day 60 defined as the time to day of death from any cause assessed for the intention-to-treat population with treatment as randomized, independent of treatment withdrawal or major protocol deviations according to the treatment policy, with subjects with no confirmed death before or at Day 60 being censored at day of withdrawal/Day 60 follow-up. The stratified log-rank test will be used to compare the treatments. The treatment difference will be expressed as a hazard ratio with 95% confidence intervals.

Key Secondary estimands

Time to sustained hospital discharge up to Day 60; The first occurrence of a score ≤ 2 whereafter the score stays ≤ 2 for the remainder of the 60 days trial period, assessed for the intention-to-treat population with treatment as randomized, independent of treatment withdrawal or major protocol deviations according to the treatment policy, with subjects who die prior to Day 60 being censored at Day 60 and subjects withdrawing due to other causes than death and not fulfilling the event being censored at the withdrawal day. The Kaplan-Meier difference in median time to sustained hospital discharge with 95% confidence intervals will be estimated.

Supplemental oxygen free days up to Day 29; For each subject the number of days between Day 1 and Day 29 with a score of ≤ 4 on the 8-point ordinal scale and with no documented use of COVID-19 related supplemental oxygen, assessed for the intention-to-treat population with treatment as randomized, independent of treatment withdrawal or major protocol deviations according to the treatment policy, with subjects who die prior to Day 29 being given the value -1 day and trial withdrawals prior to Day 29 due to other causes than death and not possible to follow-up being imputed using multiple imputation including assessments from day 1 to day 29. The Hodge-Lehmann median estimated of the difference in days between treatments with 95% confidence intervals will be estimated.

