Proportion of subjects free of respiratory failure at Day 15; The proportion of subjects with a score of ≤ 5 on the 8-point ordinal scale at Day 15, assessed for the intention-to-treat population with treatment as randomized, independent of treatment withdrawal or major protocol deviations according to the treatment policy, with subjects who die prior to Day 15 considered as respiratory failure and trial withdrawals prior to Day 15 due to other causes than death and not possible to follow-up being imputed using multiple imputation including their baseline characteristics and last known status. The difference in proportions between treatments with 95% confidence intervals will be estimated.

Proportion of subjects discharged from hospital and free of supplemental oxygen at Day 15; The proportion of subjects with a score of ≤ 2 on the 8-point ordinal scale and free of COVID-19 related supplemental oxygen use at Day 15, assessed for the intention-to-treat population with treatment as randomized, independent of treatment withdrawal or major protocol deviations according to the treatment policy, with subjects who die prior to Day 15 considered not discharged and trial withdrawals prior to Day 15 due to other causes than death and not possible to follow-up being imputed using multiple imputation including baseline characteristics and their last known status. The difference in proportions between treatments with 95% confidence intervals will be estimated.

4. Trial Design

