8.2. Efficacy Assessments

Planned timepoints for all efficacy assessments are provided in the SoA.

8.2.1. 8-point Ordinal Scale

The clinical status of COVID-19 is scored at each visit according to the 8-point ordinal scale ([Beigel et al., 2020](#)), which is an investigator evaluation of the clinical status at the first assessment of a given trial day. The clinical status of COVID-19 according to the 8-point ordinal scale must further be scored at the time of hospital discharge. For subjects hospitalized between Day 29 (Visit 31) and Day 60 (Visit 32), the clinical status of COVID-19 should be scored each time a change in clinical COVID-19 status is seen and until hospital discharge.

The 8-point ordinal scale is as follows:

1.	Not hospitalized, no limitations on activities
2.	Not hospitalized, limitation on activities and/or requiring home oxygen
3.	Hospitalized, not requiring supplemental oxygen - no longer requires ongoing medical care
4.	Hospitalized, not requiring supplemental oxygen - requiring ongoing medical care (COVID-19-related or otherwise)
5.	Hospitalized, requiring supplemental oxygen
6.	Hospitalized, on non-invasive ventilation or high flow oxygen devices
7.	Hospitalized, on invasive mechanical ventilation or ECMO
8.	Death

A subject re-admitted to the hospital for a non-COVID-19 related reason should be considered not hospitalized when scoring the clinical status of COVID-19 on the 8-point ordinal scale.

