The second key secondary endpoint, oxygen supplemental free days up to Day 29, will be defined as the number days for each subject with a score of ≤ 4 and no use of COVID-19 related supplemental oxygen. Treatment groups will be compared using the Wilcoxon rank-sum test and the treatment difference will be expressed as the Hodge-Lehmann difference in median number of days with 95% confidence intervals. All collected data post-treatment will be used. Subjects who die prior to Day 29 will be given the value of -1 day in the analysis and trial withdrawals prior to Day 29 due to other causes of death will be imputed (for each day) using multiple imputation including status for all of days 1 - 29. The cumulative distribution functions will be plotted to visualize the differences between treatment groups.

The third key secondary endpoint, subjects free of respiratory failure, will be defined as subjects with an ordinal scale score of ≤ 5 at Day 15. Treatment groups will be compared using a logistic regression model adjusting for treatment, baseline disease severity and region. All collected data post-treatment will be used to assess the scores. Subjects who die prior to Day 15 will be considered in respiratory failure and trial withdrawals prior to Day 15 due to other causes than death and not possible to follow-up will be imputed using multiple imputation taking subjects

baseline characteristics and last known status into account. The adjusted proportions as calculated from ([Ge et al., 2011](#)) and the statistics (treatment difference, SE and CI) following multiple imputation will also be presented. The ITT will be used for the analysis. The number of responders/non-responders will also be presented (these will be the non-imputed values).

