Appendix 5: Endpoint Derivation Details

Endpoint	Calculation	Handling of Death	Handling of Missing Data
All-Cause Mortality (Primary Analysis)	Date of event is the date of death Subjects without event will be censored at the time of completion/study discontinuation	n/a	n/a
All-Cause Mortality (Sensitivity Analysis including Multiple Imputation)	Proportion of deaths is the number of subjects with an ordinal scale value of 8 at Day 60	n/a	Missing data at Day 60 will be imputed.
Time to Sustained hospital discharge (Primary Analysis)	Date of event is the last date of discharge (for initial hospitalization or re-hospitalization for COVID-19 reasons) as recorded on the hospitalization form for subjects. If a subject has the event and subsequently withdraws (for reasons other than death) the subject will be treated as having the event If subject does not have event prior to completion/discontinuation the subject is censored at date of completion/discharge (for reasons other than death)	Subjects are treated as worst case (Day 60 is value used in analysis)	n/a
Time to Sustained hospital discharge (Sensitivity Analysis including Multiple Imputation)	Date of event is the last date of discharge (for initial hospitalization or re-hospitalization for any reason) as recorded on the hospitalization form for subjects with no missing data. For subjects with missing data, such that the event occurs at an imputed visit (≤ 2 ordinal scale occurs after which all subsequent visits stay at ≤ 2), time to sustained discharge will be the relative day of the imputed visit. For subject with Imputed data, if subjects discharges prior to missing data being observed and imputed values indicate the subject stays discharged (≤ 2), the last date of discharge recorded in the hospitalization form will be used For subjects with no event based on imputed and missing data, subjects will be censored at date of completion/Day 60.	Subjects are treated as worst case (Day 60 is value used in analysis)	Missing data will be multiple imputed
Number of days oxygen free up to Day 29	Sum of all ordinal scale values of 1, 3, 4 up to Day 29	Death treated as -1	Missing data will be multiple imputed

[figure not shown]
[figure not shown]

Endpoint	Calculation	Handling of Death	Handling of Missing Data

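### At a scheduled score of 1, 3 or 4, SAP 10.10 sets aside documented COVID-19 oxygen, against the protocol's two-part definition of two key secondary endpoints (at Day 15, only score 1 matters)

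*SAP*

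**What the plan says.** **Protocol.** In the key secondary estimands of Section 3, an oxygen free day needs a score of 4 or less and must be a day "with no documented use of COVID-19 related supplemental oxygen". Section 9.3.3 repeats the second condition as "no use of COVID-19 related supplemental oxygen". For the Day 15 endpoint the subject must score 2 or less and be "free of COVID-19 related supplemental oxygen use at Day 15". Section 8.2.1 describes the score as one "which is an investigator evaluation of the clinical status at the first assessment of a given trial day". Section 8.2.2 has daily oxygen need, in hospital and at home, recorded separately up to Day 29.

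**SAP, operational rules.** Section 10.10 opens its override with "If a subject has a scheduled ordinal scale score of 1, 3, or 4". It continues that where "there is evidence of supplemental oxygen usage, the value on the adjusted ordinal scale will not be changed", the investigator's judgement prevails, and it concludes that "the subject will be considered free of supplement oxygen usage on the trial day of interest". For discharged subjects on other days, recorded oxygen gives an adjusted score of 2, which is not oxygen free. Appendix 5 then derives oxygen free days as "Sum of all ordinal scale values of 1, 3, 4 up to Day 29" and defines the Day 15 responder as an adjusted score of 1. Section 10.19.1 Step 3 uses the same two rules.

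**SAP, definitions.** Appendix 1 restates both estimands with the protocol's two conditions. Sections 12.5.3.3 and 12.5.3.5 also keep two conditions, though 12.5.3.5 sends the reader to 10.10 to classify oxygen use. Section 6.1, which lists departures from the protocol, does not mention the override.

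**The concern.** The protocol makes the oxygen record a separate hurdle that a day must clear in addition to the score. Under SAP 10.10 that record cannot change the result on a day with a scheduled score of 1, 3 or 4. Hospitalized subjects are scored daily to Day 29 (SAP 10.8), so on any in-hospital day scored 3 or 4 the oxygen condition has no effect. At the Day 15 visit, the CRF asks whether a discharged subject is still on COVID-19 related oxygen, yet even a Yes is overridden by a score of 1.

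The two records can differ without either being wrong. The score reflects the first assessment of the day, so a subject scored 3 or 4 in the morning may be given oxygen later. A condition on documented use covers that case, and the override removes it.

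At stake is whether the third- and fifth-ranked tests in the hierarchy analyze the endpoints that the protocol defines, with a departure that is neither declared nor tested.

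**Working it through.** The documents state no figure for this point, so there is nothing to reproduce. The check sets the two rules side by side.

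**Inputs**
- Protocol rule (Section 3 and 9.3.3): a day is oxygen free if score ≤ 4 and no COVID-19 oxygen is documented. A Day 15 responder has score ≤ 2 and no COVID-19 oxygen.
- SAP rule (10.10, 10.19.1 Step 3, Appendix 5): a day is oxygen free if the adjusted score is 1, 3 or 4. A Day 15 responder has an adjusted score of 1. A scheduled 1, 3 or 4 is never re-mapped. A 2 becomes 1 only without oxygen.
- Planned size: 150 per arm (Protocol 9.5, SAP 8.1).

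**Step 1. COVID-19 oxygen documented on a day with a scheduled score**

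| Scheduled score | Oxygen free day, protocol | Oxygen free day, SAP | Day 15 responder, protocol | Day 15 responder, SAP |
|---|---|---|---|---|
| 1 | no | **yes** | no | **yes** |
| 2 | no | no | no | no |
| 3 | no | **yes** | no | no |
| 4 | no | **yes** | no | no |
| 5 to 7 | no | no | no | no |

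The rules disagree in three cells for oxygen free days and in one cell for Day 15. Scores 3 and 4 are in-hospital scores, so such subjects are Day 15 non-responders under either rule.

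**Step 2. No COVID-19 oxygen documented.** With no oxygen on record at all, the rules agree at every score. If the only oxygen on record is unrelated to COVID-19, a scheduled score of 1, 3 or 4 is oxygen free under both rules.

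**Step 3. Post-discharge days between visits.** Recorded COVID-19 oxygen gives an adjusted score of 2, so the day is not oxygen free under either rule. Absent readmission, the exposed post-discharge visit days up to Day 29 are at most four: Days 8, 15, 22 and 29.

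**Step 4. Illustration (constructed).** A discharged subject has COVID-19 home oxygen recorded from Day 10 to Day 20 (11 days) and a Day 15 score of 1. The protocol counts 0 of the 11 days as oxygen free and the subject as a non-responder. The SAP counts Days 10–14 and 16–20 (10 days) as oxygen days, but counts Day 15 as oxygen free and the subject as a responder.

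**Step 5. Size.** Each affected day adds 1 to that subject's oxygen free days. Each affected Day 15 subject moves an arm's proportion by 100 × 1/150 = 0.67 percentage points. The number of such subjects is not documented. Assuming k per arm:

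| k | 100 × k/150 |
|---|---|
| 1 | 0.67 |
| 2 | 1.33 |
| 5 | 3.33 |
| 10 | 6.67 |

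These are shifts within one arm. The effect on the treatment difference depends on how k differs between arms.

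**Step 6. Is it tested elsewhere?** The sensitivity analyses in SAP 12.5.3.6 are the per-protocol set, tipping point, worst case imputation and, for oxygen free days, an ANOVA. None varies the oxygen rule.

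**The case against.** The strongest defence is that the SAP is choosing between two conflicting records. By definition, scores 3 and 4 mean that no supplemental oxygen is required, and home oxygen belongs to score 2. A recorded 1, 3 or 4 is therefore itself a statement by the investigator about oxygen. The SAP gives its reason for preferring the score, the rule is pre-specified, and the change history shows it was added deliberately. Days between visits are treated differently because they have no investigator score to defer to. The override can even agree with the protocol where another part of 10.10 would not: item 4 counts concomitant oxygen without asking whether it is COVID-19 related, whereas the override leaves a subject on unrelated oxygen as oxygen free.

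Much of this stands. It shows that the rule is a reasoned choice, and that a conflicting record cannot simply be called a false oxygen free day. It does not reconcile the texts. The protocol asks about documented use as well as the score, and the score's timing means that oxygen later in the day need not contradict it. A direct Yes at the Day 15 visit is also set aside. A deliberate departure still belongs in 6.1.

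A reader might also infer that every conflicting record turns a Day 15 non-responder into a responder, or that every score of 1, 3 or 4 is exposed. Neither follows: only score 1 can change the Day 15 result, and only scheduled scores trigger the override.

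**Conclusion.** The contradiction is real but confined to days that combine a scheduled score of 1, 3 or 4 with documented COVID-19 related oxygen. There, SAP 10.10, 10.19.1 Step 3 and Appendix 5 depart from Protocol Section 3 and 9.3.3 and from the SAP's own Appendix 1. The departure is not listed in 6.1.

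The size is 1 day per affected day and, at Day 15, 0.67 percentage points per affected subject at the planned 150 per arm. The range up to 6.67 points rests on an assumed 1 to 10 such subjects in an arm and is not an estimate.

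A reader might go further and infer that the rule favors C21, or that the two endpoints are broadly invalid. The documents do not support either reading. They give no count of conflicting records and no reason to expect them to differ between blinded arms, so neither the presence nor the direction of bias can be determined. Both endpoints also follow mortality and time to sustained discharge in the hierarchy, so they carry formal weight only if the tests above them succeed. This should be corrected, but it does not touch the primary analysis.

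**What to change.** Before unblinding, amend SAP 10.10, 10.19.1 Step 3 and Appendix 5:

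- Count an observed day as oxygen free only if the adjusted score is 1, 3 or 4 and no COVID-19 related oxygen record covers that day. For the Day 15 endpoint, require an adjusted score of 1 and no such record at Day 15.
- Keep the rule in 12.5.3.3 for subjects on chronic oxygen before COVID-19.
- State whether conflicting scores are re-mapped before imputation or only when the endpoint is derived, because the adjusted scores also feed the Step 2 imputation model.
- Retain the present investigator-score rule as a sensitivity analysis.

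At minimum, list the departure in SAP 6.1 and run the protocol definition as a sensitivity analysis for both endpoints.

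The data are already collected. The cost is SAP wording, some added programming including the imputation step, and queries on conflicting records. Timing matters because a choice between records made after unblinding would be hard to defend.
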